## **12.2. Quality Audits**

Medtronic reserves the right to conduct quality audits at the Investigational Centers in order to verify adherence to external regulations as well as internal policies and procedures, to assess adequacy and effectiveness of clinical policies and procedures, to assure compliance with critical study document requirements, to confirm integrity and accuracy of clinical study data and to protect the safety, rights and welfare of study subjects.

## **12.3. Investigational Center Disqualification**

Medtronic and/or the IRB retain the right to disqualify an Investigational Center and remove all study materials at any time. Specific instances, which may precipitate Investigational Center disqualification, include but are not limited to:

- Unsatisfactory subject enrollment with regard to quality and quantity.
- Persistent non-compliance to protocol procedures on the part of an Investigator/Investigational Center. Inaccurate, incomplete, and/or untimely data recording on a recurrent basis.
- The incidence and/or severity of adverse experiences in this or other studies indicating a potential health hazard caused by the device.

A written statement fully documenting the reasons for such a termination will be provided to Medtronic, the Institutional Review Board (IRB) and other regulatory authorities, as required.

## **12.4. Protocol Deviations**

Deviations from the protocol and/or applicable regulatory requirement(s) by an Investigator/institution should lead to action by the Sponsor to secure compliance. Measures taken to secure compliance may include identifying appropriate corrective actions or additional training.

Any deviation from the procedures laid out in the protocol must be identified and documented on an eCRF. Medtronic retains the right to require the withdrawal of any subject or Investigator/Investigational Center that violates the protocol.

If monitoring and/or auditing identify serious and/or persistent non-compliance on the part of an Investigator/Investigational Center, the Sponsor should terminate the Investigator/institution's participation

in the trial. When an Investigational Center's participation is terminated because of non-compliance, the sponsor should promptly notify the IRB and the FDA.

## **13. Device Performance Issues & Complaints for the 530G Insulin Pump and CGM System**

The Medtronic 24 Hour Help Line (HL) will be consulted for device troubleshooting; they should be contacted immediately in the event of device performance problems. Subject will be instructed to notify the HL that they are currently participating in the study. All device complaints that are reported to the HL staff by the Subject will be documented by the HL staff.

The 24-Hour Helpline is responsible for handling customer complaints/customer inquiries for all approved product. The Helpline will be notified of a customer complaint/inquiry via phone, email, letter or fax. If the customer complaint/inquiry did not originate via phone then the customer service representative may initiate a follow up call with the customer as necessary.

Helpline Customer Service Representatives will receive training from the clinical study team to ensure that study subjects will be identified appropriately.

Once the complaint is received the customer service representative will identify the customer using a SA&P (Systems Application & Products - integrated software system used by Medtronic Diabetes that stores all of Medtronic Diabetes' electronic data and enables data to be shared and accessed by multiple departments) transaction and verify/update customer's information. The customer service representative will also obtain any additional information to ensure accurate documentation and to meet regulatory requirements.

The customer service representative will obtain all details of the customer's complaint/inquiry and document those details in a service notification. The representative will also select a reason code in the SA&P transaction that matches the customer complaint or inquiry. The code will also be linked to any potential product return.

In addition, the customer service representative will troubleshoot the customer's complaint or product issue according to established and validated guides. The results of troubleshooting will be documented in the service notification. Trouble shooting by Helpline will follow the standard commercial process.

The customer service representative will explain and document the outcome of troubleshooting and will advise the customer to monitor or return the product. The customer will be advised to monitor if no issue is found or be advised to replace the product if troubleshooting indicates a possible product issue.

If a return is required a return sales order will be created and return materials sent to the customer along with a replacement product (if necessary).

Information received from study subjects during Helpline calls will be provided to study doctors for review of adverse events.

## **14. Safety**

### **14.1. Potential Risks**

#### **14.1.1. Potential side effects related to insulin pump infusion set may include**

- Infection
- Skin irritation/ Redness

- Bruising
- Discomfort/ Pain
- Bleeding
- Irritation
- Rash

Investigational Centers and subjects will be instructed to follow the provided user guides for insertions and care of infusion sets. If an infusion site becomes irritated or inflamed, the infusion set should be removed and another placed in a new location.

### **14.1.2. Potential risks with insulin administration and pump use**

Due to the use of insulin, there is a potential for adverse events related to the infusion of insulin and the potential interruptions of insulin delivery. These risks all may include:

- Hypoglycemia
- Diabetic Ketoacidosis (DKA)
- Hyperglycemia
- Severe Hypoglycemia with or without associated seizure, coma or death.

### **14.1.3. Potential risks with sensor use**

Potential risks include the following:

- Skin Irritation or reaction to adhesives
- Bruising
- Discomfort
- Redness
- Bleeding
- Pain
- Rash
- Infection
- Irritation from tapes used with glucose-sensing products
- Raised Bump
- Appearance of a small "freckle-like" dot where needle was inserted
- Allergic reaction
- Syncopal episode secondary to needle insertion
- Soreness or tenderness
- Swelling at insertion site
- Sensor fracture, breakage or damage
- Minimal blood splatter associated with sensor needle removal

#### **14.1.4. Potential adverse events with serter use:**

- Skin infection around area where serter is used

#### **14.1.5. Potential risks specific to TS Feature:**

- When TS is turned ON, the feature may not activate when the blood sugar is low.
- When TS is turned ON, the feature may falsely activate when the subject's blood sugar is not low.
- The TS feature is not intended to prevent or treat hypoglycemia.

#### **14.1.6. Potential risks related to frequent finger stick testing**

- Potential risks associated with frequent meter testing of blood glucose and ketones include discomfort and bruising at tips of fingers.

#### **14.1.7. Potential risks and mitigations for young adult subject population**

The young adult subject population (16-21 years of age) has an increased risk for hypoglycemia, including severe hypoglycemia.

Standard mitigations in both young adult and adult subjects include:

- Training of primary caregivers will be conducted in addition to subject training.
- Subject instruction to test BG via finger stick testing 4-6 times a day.
- Subject instruction to adhere to 100% sensor wear.
- Subject instruction to use the bolus wizard when determining meal or correction bolus.

### **14.2. Reporting of Adverse Events**

The Medtronic Clinical Research Department, in conjunction with the Medtronic Regulatory Affairs Department, in Northridge, California will monitor and manage adverse event reporting for the study.

A complete description of the event including treatment and interventions provided by medical professionals will be included on the AE eCRF. It is expected that the investigator will provide the sponsor with the necessary medical records to support the adverse event.

Throughout the course of the study, Investigational Center staff will make all efforts to remain alert to possible reportable adverse events or untoward findings. Reports of adverse events will be requested from subjects at each visit and adverse event eCRFs will be completed as required. Investigational Center staff will assess the intensity of each adverse event and its relationship to study procedures or devices.

Adverse events that are assessed to have a relationship to a study procedure or study device will be analyzed by the Human Factors group at Medtronic Diabetes to determine whether or not there is a connection to mis-use of the device(s) or user error.

Events that are moderate and severe in intensity, all SAE, SADE and UADE that have not resolved at the time of the subject's discontinuation or completion of the study will be followed until the medical outcome is determined or until no further change in the condition is expected. All adverse events that have not resolved will have a final status of 'ongoing'.

### 14.2.1. Adverse Events Reported to Sponsor:

The Investigator or designee will report to the sponsor the following adverse events:

- Adverse Events related to the study device
- Adverse Events related to study procedures
- Serious Adverse Events (SAE)
- Unanticipated Adverse Device Effects (UADE)
- Incidence of Severe Hypoglycemia
- Incidence of Severe Hyperglycemia
- Incidence of Diabetic Ketoacidosis (DKA)

A pre-existing medical condition will only be documented as an adverse event if the condition worsens during the course of the subject's participation in the study. Non-serious Adverse events should be entered on the appropriate Electronic Case Report Form (eCRF) within 14 days of subject report to the site. For serious adverse events, reporting is required to sponsor within 24 hours of site awareness.

### 14.3. CEC Review of Events

Severe hypoglycemia, Severe Hyperglycemia, DKA and SADE will be adjudicated by the Clinical events committee (CEC) comprised of external physicians. The adjudication will include device relatedness and whether the event was considered to be serious or not. The CEC may use CareLink reports, medical records and information on CRF to make determination.

### 14.4. Definitions

#### Adverse Event (AE) (ISO14155-2)

Any untoward medical occurrence, unintended disease or injury, or untoward clinical signs (including abnormal laboratory findings) in subjects, users or other persons, whether or not related to the investigational medical device.

Note 1: This definition includes events related to the investigational medical device or the comparator.

Note 2: This definition includes events related to the procedures involved.

Note 3: For users or other persons, this definition is restricted to events related to investigational medical devices.

#### Adverse Device Effect (ADE) (ISO 14155)

Any untoward and unintended response to a medical device

Note 1: This includes any adverse event resulting from insufficiencies or inadequacies in the instructions for use, the deployment, the implantation, the installation, the operation, or any malfunction of the medical device.

Note 2: This includes any event that is a result of a use error or intentional misuse.

### **Serious Adverse Event (SAE) (ISO 14155-2)**

An adverse event that

- (a) Led to a death
- (b) Led to a serious deterioration in the health of the subject that
  - resulted in life threatening illness or injury,
  - resulted in a permanent impairment of a body structure or a body function
  - required in-patient hospitalization\* or prolongation of existing hospitalization
  - resulted in medical or surgical intervention to prevent permanent impairment to a body structure or a body function
- (c) Led to fetal distress, fetal death or a congenital abnormality or birth defect

*\*Inpatient Hospitalization is defined as: 24 hour acute admission to the hospital based on urgent medical need rather than elective admission.*

Note: A planned hospitalization for pre-existing condition, or a procedure required by the CIP, without a serious deterioration in health, is not considered to be a serious adverse event.

### **Serious Adverse Device Effect (SADE) (ISO 14155-2)**

Adverse device effect that has resulted in any of the consequences characteristic of a serious adverse event.

### **Unanticipated Adverse Device Effect (UADE) (21 CFR 812.3(s))**

Any serious adverse effect on health or safety or any life-threatening problem or death caused by, or associated with, a device, if that effect, problem, or death was not previously identified in nature, severity, or degree of incidence in the investigational plan or application (including a supplementary plan or application), or any other unanticipated serious problem associated with a device that relates to the rights, safety, or welfare of subjects.

**Severe Hypoglycemia** is an event requiring assistance of another person to actively administer carbohydrate, glucagon, or other resuscitative actions. These episodes may be associated with sufficient neuroglycopenia to induce seizure or coma. Plasma glucose measurements may not be available during such an event, but neurological recovery attributable to the restoration of plasma glucose to normal is considered sufficient evidence that the event was induced by a low plasma glucose concentration. **(American Diabetes Association Workgroup on Hypoglycemia, Diabetes Care 28:1245-1249, 2005)**

**“Severe Hyperglycemia”** is defined as Hyperglycemia (blood glucose >300 mg/dL) with blood glucose ketones >0.6mmol/L, urine ketones moderate or large, or accompanied by symptoms of nausea, vomiting or abdominal pain.

**“Diabetic Ketoacidosis/DKA”** is defined as: Hyperglycemia (blood glucose greater than 250 mg/dL or greater than 13.9 mmol/L) with either low serum bicarbonate (less than 15 mEq/L) and/or low pH (less than or equal to 7.24) Anion gap (greater than 12) and either ketonemia or ketonuria and requiring treatment within a health-care facility. **(American Diabetes Association-Diabetes Care, Volume 27, Supplement 1, January 2004)**

## **14.5. Device or Procedure Relatedness:**

The relatedness of the event to the study device or procedures will be determined for each adverse event. Subjects participating in this study have diabetes that is insulin requiring and it is expected that due to the disease subjects will have adverse events that are part of their disease. It is expected that the investigator

will assess all events to determine if the event was related to the disease or if the event was related to the device or study procedure. An adverse event is not automatically related to the study device or procedure simply because the subject is wearing the device and participating in the study. The event should be reviewed to determine if the device or study procedure could have possibly caused the event and therefore is related to the study device or procedure.

The investigator will review all elements surrounding the event to properly determine relatedness – this would include the subjects description of the event, study device downloads and medical records (if applicable) from the treating facility. These records will be made available to the sponsor and the Clinical Events Committee at the request of the sponsor. The following definitions should be considered when determining the relationship of the event to the device or study procedure:

- Causal relationship – clearly related to the device or procedure
- Probable – likely related to the device or procedure
- Possible – may be related to the device or procedure
- Unlikely – doubtfully related to the device or procedure
- Not Related – clearly not related to the device or procedure
- Unknown – not enough information exists to determine

If the investigator determines the event meets the definition of definite, probable or possible the event should be considered related and the Yes box on the AE eCRF would be checked for the question related to. If the investigator determines the event meets the definition of unlikely, not related or unknown the event should be considered unrelated and the NO box would be checked on the AE eCRF for the question was the event related to.

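### Coding unknown relatedness as unrelated lowers the related adverse event counts and keeps some events out of Human Factors and CEC review

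*Protocol*

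**What the plan says.** Protocol 14.5 gives six levels of relatedness to the device or procedure: causal, probable, possible, unlikely, not related and unknown. The last applies when "not enough information exists to determine". The six levels are then reduced to one Yes/No box. For the upper levels the wording is "definite, probable or possible the event should be considered related and the Yes box on the AE eCRF would be checked". For the rest it is "unlikely, not related or unknown the event should be considered unrelated", and the NO box is ticked.

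Other parts of the plan use this judgement or work alongside it:

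- Protocol 14.2.1 has a list introduced by "The Investigator or designee will report to the sponsor the following adverse events". Two lines depend on relatedness: "Adverse Events related to the study device" and the matching line for study procedures. The other lines are SAEs, UADEs and three glycemic events. The glycemic lines, such as "Incidence of Severe Hypoglycemia", carry no condition on relatedness or seriousness.
- Protocol 14.2 says that "Adverse events that are assessed to have a relationship to a study procedure or study device will be analyzed by the Human Factors group", to look for misuse or user error.
- Protocol 14.3 sends severe hypoglycemia, severe hyperglycemia, DKA and SADEs to the CEC, which judges device relatedness and seriousness.
- Protocol 7.1.4 and SAP 7.2.2 summarise device-related and procedure-related events among those that sites report. Neither text mentions an unknown category.

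**The concern.** An event that cannot be judged for lack of information is not one judged to be unrelated. The rule gives both the same code. It also fits poorly with the low bar that 14.5 sets elsewhere: if the device or procedure might have caused the event, it counts as related, and the level 'possible' is coded Yes. An event too poorly documented to assess has not been shown to fail that test.

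The study exists for ongoing surveillance of the Threshold Suspend feature (Protocol 3). Two things are at stake. The related counts lean one way, because the rule can remove events from them but never add any. And the events with the least information are the ones left out of reviews that might supply it.

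**Working it through.** The plan states no figure on this point, so the check traces the code through the text.

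**Step 1: the count.** Let R be the number of events judged causal, probable or possible, and U the number judged unknown.

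- Coded related count under 14.5: R
- Count with unknown events included: R + U
- Relative shortfall: (R + U − R)/(R + U) = U/(R + U)

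R + U is the count under the opposite convention, not the true number of related events. The documents give neither R nor U.

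**Step 2: where an event of unknown relatedness goes once it is coded NO.**

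| Event of unknown relatedness | On the 14.2.1 list | CEC (14.3) | Human Factors (14.2) |
|---|---|---|---|
| Severe hypoglycemia, severe hyperglycemia, DKA | Yes, whatever the relatedness | Yes, including device relatedness | Not on the investigator's code |
| Other serious event | Yes, as an SAE | No, because not a SADE | No |
| Other non-serious event | No line covers it | No | No |

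The second row follows from the definitions in 14.4. A SADE is an adverse device effect with serious consequences, and an adverse device effect is a response to the device. An event recorded as unrelated does not meet that definition.

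**Step 3: whether the third row means that the event is never recorded.** Two readings stand side by side.

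- *Not reported:* the 14.2.1 list covers non-serious, non-glycemic events only if they are related.
- *Entered:* 14.2.1 also asks for non-serious events on the eCRF within 14 days, without a relatedness condition. The recording instruction in 11.2.1, repeated for later visits, has none either. The NO box in 14.5 presupposes that unrelated events are entered.

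The text does not settle which reading applies.

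**Step 4: the planned confidence limits.** The one-sided 95% upper limits for DKA and severe hypoglycemia (Protocol 7.1.4, SAP 7.2.2) are defined on incidence. Relatedness does not enter them.

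**The case against.** The strongest reply is that the events most closely tied to insulin suspension are protected. Severe hypoglycemia, severe hyperglycemia and DKA are reported and adjudicated for device relatedness whichever box the investigator ticks. No hypothesis test uses related counts, and the adverse event analysis is descriptive. All of this stands, and it limits the point to descriptive counts and review routing.

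Second, because 'possible' already counts as related and the investigator must review the subject's account, device downloads and any medical records, unknown should be a small residual. That is plausible, but the documents give no frequency.

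Third, HelpLine complaints are documented, passed to study doctors for adverse event review (Protocol 13) and summarised (SAP 7.2.4.6). This is another route for use-error signals. It depends on the subject calling and does not replace Human Factors review.

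Fourth, coding unknown as Yes would swap one unsupported default for the opposite one and could inflate the related counts. This is right, and the fix below does not do it.

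A reader might also infer that non-serious events of unknown cause are simply dropped from sponsor reporting. The documents do not support that: the three glycemic events stay reportable, and for the others the eCRF-entry wording points the other way. Nor do the documents support reading the rule as designed to favour the sponsor. Only its direction can be shown.

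**Conclusion.** The point holds as a modest defect in safety coding and reporting. Under 14.5, missing information is recorded as no relationship. The investigator-coded related count is lower by U/(R + U) than one that includes unknown events. All such events miss Human Factors review on that code, and serious non-glycemic ones also miss CEC adjudication, though they are still reported as SAEs. Whether other non-serious unrelated events are entered is an inconsistency to resolve, not a demonstrated loss.

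No size can be given. A reader might assume, say, 20 related and 5 to 15 unknown per 100 events and obtain 5/25 = 20% to 15/35 = 43%. Neither share is in the documents, and the result measures the true understatement only if every unknown event is in fact related.

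The conclusion rests on these assumptions:

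- The Yes/No box decides what counts as related for the tables, Human Factors review and SADE status. The documents imply this but do not say it outright.
- For the glycemic events, the documents do not say whether the CEC's or the investigator's judgement of relatedness is tabulated.
- The documents do not show whether the six-level judgement is stored or only the box.
- SAP pages 20 to 52 carry only page headers in the copy read, so any table layouts there could not be checked for an unknown row.

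**What to change.** 1. In Protocol 14.5, keep unknown as its own category instead of recording it as NO. In the same edit, align the term 'definite' in the coding rule with 'causal relationship' in the list of levels.
2. In SAP 7.2.2, show unknown as a separate row in the device-related and procedure-related tables, and give related counts with and without it. The SAP governs the final report, so this can be added there.
3. Include events of unknown relatedness in the existing Human Factors review, and serious ones in the existing CEC review.
4. Reconcile the 14.2.1 list with the eCRF-entry wording in 11.2.1 and 14.2.1, and state whether non-serious events of unknown relatedness are reported to the sponsor.

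The cost is wording, one table row and a few more events to review. All 426 subjects are already enrolled, so if only Yes/No was captured, sites must be queried to separate unknown from the other NO entries. Source documents are retained (Protocol 15.1) and electronic queries are already in use (15.2). The downside is slightly less favourable related counts where unknown events are included.
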